10.3 Statistical Methods

10.3.1 Analysis Sets

The statistical analysis will primarily be based on the Per Protocol analysis set consisting of the patients without major protocol violations. The TWPI-SHP data will also be analyzed on the Intention to Treat set.

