1.8 Patient Population

The following analysis sets are considered for the analysis:

Intention to Treat (ITT) Set: All patients enrolled in the study, who received at least one dose of adalimumab, and for whom any follow-up data are available.

Per Protocol Set (PPS): All patients of the ITT Set without any major protocol deviations. Protocol deviations will be reviewed and classified as minor or major during a data review that will be held before database lock.

Safety Set: All patients enrolled in the study, who received at least one dose of adalimumab, and for whom any follow-up data are available.

All baseline and efficacy data will be analysed on the basis of the PPS. In case the difference between the ITT Set and PPS exceeds 10% of the patients of the PPS, the TWPI data will also be analysed for the ITT Set.

The analysis of adverse events and of the course of the study will be performed on the basis of the Safety Set.

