4. COURSE OF THE STUDY

The analysis is performed for all patients and broken down by indication.

Study duration and study termination

- Descriptive statistics for study duration.
- Frequency distribution for reason for study termination.

Adalimumab treatment

- Descriptive statistics for treatment duration.
- Frequency distribution of any change in adalimumab treatment.
- For the patients for whom any change in adalimumab treatment was recorded, list of the data recorded concerning adalimumab treatment.

Concomitant Medications

- Frequency distribution of subjects taking other AS/PsA medication by WHO-DRUG anatomical class.
- Frequency distribution of subjects taking other AS/PsA medication by WHO-DRUG anatomical and therapeutic class.

Employment Situation

- Frequency distribution of any change in employment situation.
- For the patients for whom any change in employment situation was recorded, list of the data recorded at each visit concerning employment situation.

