5. EFFICACY DATA

5.1 WPAI Questionnaire

- Frequency distribution of professional activity at baseline, at each visit, and at the last observation.
- Frequency distribution of professional activity at each visit and at the last observation, broken down by professional activity at baseline.

For absenteeism, presenteeism, TWPI, and percentage activity impairment:

- Descriptive statistics at baseline, at each visit, and at the last observation.
- Descriptive statistics of the change between baseline and each visit, and between baseline and the last observation.

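### The ITT analysis is limited to TWPI, so the return-to-work and job-loss tables in SAP 5.1 exist on the Per Protocol Set only

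*SAP*

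**What the plan says.** **Analysis sets.** SAP 1.8 states: "All baseline and efficacy data will be analysed on the basis of the PPS". The ITT Set enters only under a condition: "In case the difference between the ITT Set and PPS exceeds 10% of the patients of the PPS", then "the TWPI data will also be analysed for the ITT Set". Protocol 10.3.1 carried no condition: "The TWPI-SHP data will also be analyzed on the Intention to Treat set".

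**Employment by visit.** SAP 5.1, under Efficacy Data, plans a "Frequency distribution of professional activity at baseline, at each visit, and at the last observation", and the same item broken down by professional activity at baseline. As efficacy data, both fall on the PPS.

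**Employment changes from the CRF.** SAP 4 plans a "Frequency distribution of any change in employment situation", plus a by-visit list for patients with a change. For the set, SAP 1.8 says: "The analysis of adverse events and of the course of the study will be performed on the basis of the Safety Set". It defines that set as follows: "Safety Set: All patients enrolled in the study, who received at least one dose of adalimumab, and for whom any follow-up data are available". The ITT Set has the same definition.

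**Missing-score rule.** Under SAP 1.9, if WPAI Question 1 (having a professional activity) is not answered yes, any answers to Questions 2 to 5 are treated as missing.

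**The concern.** Whether patients return to work on adalimumab is one of the questions listed under the main objective (Protocol 5.1, SAP 1.2.1). The number employed at each visit is a secondary endpoint (Protocol 5.4, SAP 1.2.2). The table that answers the question is the breakdown of professional activity by baseline activity, and it is planned only for patients without major deviations. Deviations are classified as minor or major at a data review before database lock, so the SAP itself does not fix who is left out. If excluded patients lose work more often, or return less often, than those retained, the PPS gives too favourable a picture. The one ITT analysis in the plan is of a variable that does not exist for patients out of work.

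**Working it through.** **1. The plan's own figures.** SAP 1.4 has 200 patients, 65% working, and 80% of those with 18-month data: 200 × 0.65 × 0.80 = 104, stated as about 100. With n = 100 and t(0.975, 99) = 1.984, the half-widths are 1.984 × 23.8/10 = 4.72 and 1.984 × 30.0/10 = 5.95, which reproduce all six intervals in the table. These figures concern TWPI; the plan gives no precision for employment.

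**2. Can TWPI register a change in employment?** SAP 1.6 computes it from Questions 2, 4 and 5.
- A worker who stops has Question 1 = no at follow-up, so Questions 2 to 5 are missing and there is no follow-up TWPI and no change.
- A non-worker who returns has no baseline TWPI and so no change.
- The last-observation rule in SAP 1.9 does not help. It takes the last visit at which any item of the questionnaire was completed. A patient who answers no to Question 1 is sent on to Question 6, so that visit counts and holds no TWPI.
- The table will show a count of missing values (SAP 1.7), but that count mixes job loss with other reasons for missing data.

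If 5%, 10% or 20% of the 104 followed workers stopped (assumed rates), about 5, 10 or 21 would leave the TWPI change, leaving about 99, 94 or 83. Absenteeism and presenteeism use the same questions and go missing in the same way. Only Question 1 and the CRF employment status register the event.

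**3. Which employment output is on which set?**

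| Output | Set | Gives direction and denominator? |
|---|---|---|
| SAP 3.3 baseline employment status | PPS | baseline only |
| SAP 5.1 professional activity, by visit and by baseline activity | PPS | yes |
| SAP 4 change frequency | Safety (same as ITT) | no |
| SAP 4 listing | Safety (same as ITT) | direction by patient, no rates |

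The CRF employment block in SAP 1.5 also covers job content, occupational situation and part-time work, so a recorded change need not be a move into or out of work. Baseline employment is tabulated on the PPS, so rates on the larger set cannot be formed from the planned tables.

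**4. The 10% trigger.** It fires when e/(N − e) > 0.10, where e is the number excluded. For N = 200: 18/182 = 9.9% does not fire; 19/181 = 10.5% does. Assume 65% employed in a PPS of 182, about 118 patients (118/182 = 64.8%). The ITT rate then lies between 118/200 = 59.0% (none of the 18 employed) and 136/200 = 68.0% (all employed).

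**5. Illustration when the trigger fires (all exclusion and event counts assumed).** PPS 160, so 40/160 = 25%.
- PPS: 12 of 56 non-workers return (21.4%) and 8 of 104 workers stop (7.7%). Employment goes from 104/160 = 65.0% to (104 − 8 + 12)/160 = 67.5%.
- Excluded: none of 14 non-workers return; 8 of 26 workers stop.
- ITT: 12/70 = 17.1% return and 16/130 = 12.3% stop. Employment goes from 130/200 = 65.0% to (130 − 16 + 12)/200 = 63.0%.

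With the 40 excluded patients' final status left open, the ITT figure could be anything from 108/200 = 54.0% to 148/200 = 74.0%.

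**The case against.** The strongest reply is that employment is already reported on an ITT-equivalent set. SAP 4 lists every patient with a recorded change, and the CRF fields include unemployment, retirement and whether these are due to the disease. This stands in part. A reader might infer that all employment results are Per Protocol only and that job loss among excluded patients would be invisible; the documents do not support that, because the listing could show individual cases. What is missing is a directional summary with rates.

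Three other stronger readings also fail.
- TWPI is not the only work score that cannot register job loss; absenteeism and presenteeism behave identically, so rerunning them on the ITT Set would not help here.
- The SAP 4 and SAP 5.1 employment outputs should not be expected to agree even on one set, because the CRF employment situation and WPAI Question 1 are different variables.
- It is not established that the SAP narrowed the protocol's scope. The protocol's term TWPI-SHP is undefined and could mean TWPI or the whole WPAI-SHP. SAP 1.10 reads it as TWPI, and limiting a sensitivity analysis to the primary endpoint is conventional.

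The reversal in the illustration was also chosen to occur: excluded workers stop at 8/26 = 30.8% against 7.7% in the PPS. Approximate paired 95% intervals for the change are −3.0 to 8.0 points (PPS) and −7.2 to 3.2 points (ITT); both include zero and they overlap widely. Finally, the study is descriptive and employment is a secondary endpoint.

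**Conclusion.** The point holds as a gap in coverage. The return-to-work and job-loss rates are planned on the PPS alone, the ITT analysis is confined to a variable that is missing for anyone not working, and the SAP 4 output on the equivalent set is undirected or unsummarised. This follows from the text of SAP 1.8, 1.9, 4 and 5.1 without assumptions.

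Its size is not known, because the documents do not say how many patients the PPS will exclude or what became of their work. The 59.0% to 68.0% range is a bound under an assumed 65% employment in the PPS. The movement from a 2.5-point rise to a 2.0-point fall shows only that a reversal is possible, and it assumes that final status is known for all 200 patients. SAP 1.10 reports that an important proportion left before Month 18, and an ITT table would not cure that. The primary TWPI analysis is unaffected. This is a cheap and worthwhile improvement on a stated study question.

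**What to change.** In SAP 1.8, add that the professional-activity tables of Section 5.1 (by visit and at the last observation, including the breakdown by professional activity at baseline) will be presented on the ITT Set alongside the PPS, whether or not the 10% difference is reached. Adding them inside the existing conditional sentence would not be enough, since up to 18 exclusions out of 200 would leave them unproduced. A footnote should say that these tables use WPAI Question 1 and are not expected to match the CRF employment changes in Section 4.

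The cost is one sentence in the SAP and a few extra tables from programs that already have to be written. No new data are needed.

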1.9 Data Handling

The following data handling transformations are performed for the analysis:

Onset data

- Date of enrolment is taken to be date of informed consent

WPAI Questionnaire

- For patients with (number of hours missed due to psoriasis = number of hours worked = 0), Absenteeism, Presenteeism and Total work productivity impairment are set to missing.
- If the answer to Question 1 of the WPAI Questionnaire is not YES but there is an answer to any of Questions 2, 3, 4, or 5, then the answers to these questions are considered to be missing.

Serious Adverse Events

In case of a partial or missing date for the start of a serious adverse event it will be

assumed that the event was study-emergent unless it can be determined from the partial start or stop date that the event definitely started before the date of informed consent or more than 70 days after the last administration of study medication.

Last Observation and Last Attended Visit

The analysis of individual scales is performed for each visit and for the last observation after baseline. For multi-item questionnaires the last observation after baseline is defined as the observation for the last visit after baseline at which any of the items of the questionnaire is completed.

The analysis of the relation between variables is performed for data recorded at baseline, at Month 18, and at the last attended visit.

Other Missing Data

No other estimation will be performed of missing data. In order to obtain estimates for the end of the study, use is made of the last observation after baseline. If date of completion/withdrawal was missing it has been set to date of last contact.

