APPENDIX C: Health Assessment Questionnaire Disability Index (HAQ-DI)

In this section we are interested in learning how your illness affects your ability to function in daily life.

Please tick the response which best describes your usual abilities OVER THE PAST WEEK:

Without ANY Difficulty	With SOME Difficulty	With MUCH Difficulty	UNABLE To Do
------------------------------	-------------------------	----------------------------	-----------------

DRESSING & GROOMING

Are you able to:

- Dress yourself, including tying shoelaces and doing up buttons?
- Wash your hair?

RISING

Are you able to:

- Stand up from a straight chair?
- Get in and out of bed?

EATING

Are you able to:

- Cut up your meat?
- Lift a full cup or glass to your mouth?
- Open a new milk carton ?

WALKING

Are you able to:

- Walk outdoors on flat ground?
- Climb up five steps?

Please tick the response which best describes your usual abilities **OVER THE PAST WEEK**:

Without ANY Difficulty	With SOME Difficulty	With MUCH Difficulty	UNABLE To Do
------------------------------	----------------------------	----------------------------	-----------------

HYGIENE

Are you able to:

- Wash and dry your body?
- Have a bath?
- Get on and off the toilet?

REACH

Are you able to:

- Reach up for and take down a 5 lb object (e.g.: a bag of potatoes) from just above your head?
- Bend down to pick up clothing from the floor?

GRIP

Are you able to:

- Open car doors?
- Open jars which have been previously opened?
- Turn taps on and off?

ACTIVITIES

Are you able to:

- Go shopping?
- Get in and out of a car?
- Do chores such as vacuuming and gardening?

APPENDIX D: Work Productivity and Activity Impairment - Specific Health Problem Questionnaire (WPAI-SHP)

The following questions ask about the effect of your **DISEASE (Ankylosing Spondylitis = AS or Psoriatic Arthritis = PsA)** on your ability to work and perform regular activities. *Please fill in the blanks or circle a number, as indicated.*

1. Are you currently employed (working for pay)? _____ NO _____ YES
If NO, check "NO" and skip to question 6.

The next questions are about the **past seven days**, not including today:

2. During the past seven days, how many hours did you miss from work because of problems associated with your AS or PsA? *Include hours you missed on sick days, times you went in late, left early, etc., because of your AS or PsA:*

_____ HOURS

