1.4 Sample Size Justification

The main objective of this study is to observe the working status in AS and PsA patients before and after the start of adalimumab therapy in daily practice. The primary variable is the change in total work productivity impairment (TWPI) due to AS/PsA between baseline and Month 18. The change will be evaluated in a descriptive way by means of the mean change observed in the study and its 95% confidence interval.

The number of patients to be enrolled (200) was determined on the basis of the recruiting capacity of the participating investigational sites during the foreseen recruitment period of 12 months.

Based on data from Reilly et al¹ it is estimated that about 65% of the patients of the study population are working and therefore evaluable for work productivity impairment.

Supposing that 80% of the employed patients have data available over an 18 month period, the mean change in TWPI will be estimated on the basis of data for about 100 patients.

Based on data for a 16 week treatment period it is estimated that the standard deviation of the change in TWPI will be about 23.8. Since the estimate to be made is for an 18 month treatment period, 95% confidence intervals are also calculated for a somewhat more important standard deviation, arbitrarily set equal to 30.0.

¹ Reilly MC, Zbrozek AS, Dukes EM. The validity and reproducibility of a work productivity and activity impairment instrument. *Pharmacoeconomics*. 1993; 4: 353–65.

The table below contains 95% confidence intervals on the mean change for some possible mean changes (-10.0, -15.0 and -20.0), and for standard deviations (SD) of 23.8 and 30.0, supposing data will be available for 100 patients:

Mean change	SD	95% CI
-10.0	23.8	[-14.7 ; -5.3]
-15.0	23.8	[-19.7 ; -10.3]
-20.0	23.8	[-24.7 ; -15.3]
-10.0	30.0	[-16.0 ; -4.0]
-15.0	30.0	[-21.0 ; -9.0]
-20.0	30.0	[-26.0 ; -14.0]

These intervals show that quite precise estimates can be obtained of the change in TWPI on the basis of the planned sample size.

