1.5 Study Data Considered for the Analysis

The following data are used for the analysis:

Data only collected at screening (baseline)

- Date of inclusion (screening) and date informed consent form was signed
- Demographic data
 - Year of birth
 - Gender
 - Ethnic origin (Caucasian, Hispanic, Black, Asian, Other).
- Indication for adalimumab therapy (ankylosing spondylitis, psoriatic arthritis) and year of diagnosis.
- Extra-articular disease manifestations: None or
 - Psoriasis
 - Inflammatory bowel disease
 - Uveitis
For each manifestation: Yes/no and (currently active, currently inactive)
- Smoking status (never smoked, ex-smoker, smoker, unknown)
- Other medical history: None or
 - Cardiovascular diseases
 - Cardiovascular risk factors
 - Diabetes
 - Renal disease
 - Hepatic disease
 - Lung disease
 - Mental disorders
 - Other and specification
- Medication history
 - Analgesics
 - NSAIDs

- DMARDs
- Steroids
- Biologic therapy.
- Education background (highest level achieved): None, primary school, secondary school, higher education (non-university), university.
- Start date adalimumab therapy.

Data collected at each visit

- Date of visit
- Employment situation (to be answered at baseline, and at each follow-up visit in case of any change since the last visit):
 - Current employment status:
 - Housewife/houseman, due to As/PsA (yes, no)
 - Unemployed, due to As/PsA (yes, no)
 - Retired, due to As/PsA (yes, no)
 - Part-time employed: Percentage, due to As/PsA (yes, no)
 - Full-time employed
 - Student.
 - Current job content:
 - Professional or technical
 - Administrative or managerial
 - Sales
 - Service tasks
 - Agricultural
 - Production/manufacturing, transport equipment operator, laborer
 - Armed forces
 - Other and specification.
 - Current occupational situation:
 - Employee
 - Independent
 - Public/civil servant
 - Volunteer
 - Other
- Disease activity measures and clinical evaluations:
 - Only PsA
 - Body Surface Area (BSA) affected (no psoriatic lesions, <3%, 3-10%, 11-20%, >20%).
 - DAS28 score.
 - Only AS
 - BASDAI
 - Consists of 6 items assessed on ordinal scales. Higher scores indicate higher severity. The scores for Items 1 to 5 are integers between 0 and 10. The scores for Item 6 is a continuous assessment between 0 and 10.
 - The total score is calculated as:
[(Item 1+Item 2+Item 3+Item 4)+(Item 5+Item 6)/2]/5

PsA and AS

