- The assignment of aids and devices to categories is done as follows:

Aid or device	Associated with category
Cane, walker, crutches, wheelchair	Walking
Devices used for dressing	Dressing and grooming
Built up or special utensils	Eating
Special or built up chair	Arising
Raised toilet seat	Hygiene
Bath tub seat	Hygiene
Jar opener (for jars previously opened)	Grip
Bath tub bar	Hygiene
Long-handled appliances for reach	Reach
Long-handled appliances for bathroom	Hygiene

- No aids or devices are assigned to the category 'Activities'.
- Aids and devices specified in the 'Other' field will not be used in the calculations.
- Help from another person for errands and chores is assigned to the category 'Activities'.
- Help from another person for gripping and opening things is assigned to the category 'Grip'.
- WPAI Questionnaire:
 - Absenteeism = Percentage work time missed due to disease = $100 \times Q2 / (Q2+Q4)$
 - Presenteeism = Percentage impairment while working due to the disease = $100 \times Q5 / 10$
 - Total work productivity impairment (TWPI) due to disease = Absenteeism (%) + extent to which the disease decreased productivity (%) x [number of hours worked /(number of hours work missed due to the disease + number of hours worked)] = $100 \times Q2 / (Q2+Q4) + 100 \times [1 - Q2 / (Q2 + Q4)] \times [Q5 / 10]$
 - Percentage activity impairment due to disease = Extent to which the disease affected the ability to perform usual daily activities = $100 \times Q6 / 10$
- Dermatology Life Quality Index (DLQI) questionnaire
 - In case one question is unanswered it is given a score of 0. In case 2 or more questions are unanswered the DLQI score is not calculated. Question 7 is considered unanswered if both parts are unanswered.
 - The DLQI score is calculated as the sum of the scores of the individual questions.

- DLQI category
 - o 0-1: No effect
 - o 2-5: Small effect
 - o 6-10: Moderate effect
 - o 11-20: Very large effect
 - o 21-30: Extremely large effect.
- Regrouped DLQI category
 - o ≤ 5
 - o > 5
- DLQI scales
 - o Symptoms and feelings: Sum of scores of Questions 1 and 2
 - o Daily activities: Sum of scores of Questions 3 and 4
 - o Leisure: Sum of scores of Questions 5 and 6
 - o Work and school: Score of Question 7
 - o Personal relationships: Sum of scores of Questions 8 and 9
 - o Treatment: Score of Question 10.

NOTES:

1. If any question associated with a scale is unanswered the corresponding scale is not calculated.

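### The SAP's WPAI rule, as written, deletes Q2 to Q5 when Q1 is merely unanswered, so a TWPI that could be computed is lost to the primary change analysis

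*SAP*

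**What the plan says.** SAP section 1.9 (Data Handling) gives two rules for the WPAI questionnaire. The one at issue reads "If the answer to Question 1 of the WPAI Questionnaire is not YES but there is an answer" to any of Questions 2 to 5, "then the answers to these questions are considered to be missing". Q6 (activity impairment) is not touched. The section later adds "No other estimation will be performed of missing data", so nothing restores the deleted answers.

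Four other places bear on the point:

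- **Formula.** SAP section 1.6 defines "Total work productivity impairment (TWPI) due to disease = Absenteeism (%) + extent to which the disease decreased productivity", weighted by the share of hours worked. Its inputs are Q2, Q4 and Q5.
- **Primary variable.** SAP section 1.4: "The primary variable is the change in total work productivity impairment (TWPI) due to AS/PsA between baseline and Month 18". Both visits are needed.
- **Questionnaire.** In protocol Appendix D, a patient who answers NO to Q1 is told to tick NO "and skip to question 6". There is no skip for a patient who gives no answer.
- **Separate employment record.** SAP section 1.5 lists "Employment situation (to be answered at baseline, and at each follow-up visit in case of any change since the last visit". Section 1.9 does not use this record to resolve a blank Q1.

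**The concern.** The condition covers two situations that call for different handling.

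If Q1 is NO and hours are reported, the form contradicts itself. The questionnaire told the patient to skip those items, so setting them to missing is defensible.

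If Q1 is blank and Q2 to Q5 are filled in with Q4 above 0, the form shows no contradiction. The patient has completed the section meant for people in work and has reported working in the past seven days. Only the gate question was left unticked. Deleting the answers here discards primary-endpoint information that was collected. One unticked box at either baseline or Month 18 is enough to remove the patient from the primary analysis.

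**Working it through.** **1. Is a blank Q1 caught by the rule?** The condition is that Q1 is not YES, rather than that Q1 is NO. A blank meets it, and section 1.9 makes no exception for an unanswered Q1.

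**2. Is TWPI computable without Q1?** With a = Q2/(Q2 + Q4), SAP section 1.6 gives TWPI = 100 × a + 100 × (1 − a) × Q5/10. Q1 does not appear. Take illustrative answers (assumed, not from the documents) Q2 = 8, Q4 = 30, Q5 = 4, with Q1 blank:

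- a = 8/38 = 0.2105
- TWPI = 21.05 + 100 × 0.7895 × 0.4 = 21.05 + 31.58 = 52.6%

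The rule turns this 52.6% into a missing value.

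**3. The plan's own precision figures.** From SAP section 1.4: 200 enrolled, 65% working, 80% of those with 18-month data, SD of the change 23.8 or 30.0.

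- Evaluable patients: 200 × 0.65 × 0.80 = 104, stated as about 100.
- Half-width = t(0.975, 99) × SD/√100, with t = 1.984.
- SD 23.8: 1.984 × 2.38 = 4.72. SD 30.0: 1.984 × 3.00 = 5.95.

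These half-widths reproduce all six intervals in the table; for example, −10.0 ± 4.72 gives −14.7 to −5.3.

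**4. Size of the loss.** The documents give no rate of blank Q1. Assume a share b of otherwise complete forms has Q1 blank at each visit, independently at baseline and Month 18. The share of pairs lost is 1 − (1 − b)², and the half-width is recomputed with the remaining n.

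| b per visit | Pairs lost of 100 | Half-width, SD 23.8 | Half-width, SD 30.0 |
|---|---|---|---|
| 0 | 0 | 4.72 | 5.95 |
| 1% | 2.0 | 4.77 | 6.01 |
| 2% | 4.0 | 4.82 | 6.08 |
| 5% | 9.8 | 4.98 | 6.27 |
| 10% | 19.0 | 5.26 | 6.63 |

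At 1% to 5% the half-width grows by 0.05 to 0.26 points at SD 23.8. Each row is a ceiling for its rate of blank Q1 overall: a patient who skips Q1 together with the rest of the work section has nothing for the rule to delete.

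**5. The last-observation analysis.** Section 1.9 takes the last post-baseline visit with any item of the questionnaire completed. Because Q6 survives the rule, a visit with Q1 blank can be selected as the last observation while its TWPI is missing. Read literally, an earlier usable TWPI would then not be used.

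**The case against.** The strongest reply is that the point is hypothetical. No document shows a single form with Q1 blank and Q4 above 0, so a reader who infers that valid data were in fact lost goes further than the text allows. Bias is not shown either. A much larger source of missing Month 18 data is documented: SAP section 1.10 reports that an important proportion of patients dropped out. All of this stands and limits the size of the point.

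Other parts of the reply also stand, wholly or in part:

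- **Upstream checks.** Protocol sections 8.0 and 9.0 provide for CRF review for completeness, source access and a change-form route. Some blanks may be resolved before the rule applies, though this is not assured for a form the patient completes.
- **Intended meaning.** For the DLQI the SAP refers explicitly to unanswered questions; here it does not. The authors may have meant only NO. If so, the text should say so, and the same edit settles it.
- **Hours worked do not prove paid work.** Q1 in Appendix D asks about working for pay, and the CRF lists volunteers and students. Setting Q1 to YES because Q4 is above 0 would therefore be unsafe.
- **CRF status is not a fresh confirmation at each visit.** After baseline it is recorded only on change, so at Month 18 an earlier value must be carried forward, and an empty field could mean no change or not completed.

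A reader might also infer that the rule removes patients from the count of those employed. It does not. The rule leaves Q1 alone, and any loss from the professional-activity table in SAP section 5.1 ("Frequency distribution of professional activity at baseline, at each visit, and at the last observation") comes from the blank itself. CRF employment is also reported separately in SAP sections 3.3 and 4.

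None of this explains why an unanswered gate question should erase answered items that suffice for the primary endpoint.

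**Conclusion.** The point holds as a defect in a written rule: read literally, it discards a TWPI that can be computed when Q1 is unanswered and hours worked are reported. It does not extend to Q1 = NO with hours reported, where the answers conflict.

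The effect is probably small. On assumed blank rates of 1% to 5% per visit, about 2 to 10 of 100 pairs are lost, and the half-width rises from 4.72 to 4.77–4.98 (SD 23.8) or from 5.95 to 6.01–6.27 (SD 30.0). This rests on independence between visits, on otherwise complete forms, and on no prior resolution by CRF review. The correction is minor but worth making, because it is cheap and concerns the primary endpoint.

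**What to change.** Amend SAP section 1.9 as follows:

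- Restrict the deletion of Q2 to Q5 to forms where Q1 is NO.
- Where Q1 is unanswered and Q4 is above 0, keep Q2 to Q5 for absenteeism, presenteeism and TWPI, unless the most recently recorded CRF employment situation shows that the patient is not in paid work. At follow-up this means carrying the last recorded status forward.
- Leave Q1 itself missing in the professional-activity table; do not infer a YES.
- Report the number of affected records by visit.

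No branch is needed for TWPI when Q4 is missing, since TWPI cannot then be computed whatever the employment status.

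The cost is a few sentences and a few lines of code, with no new data. The downside is that a small number of records will rest on a carried-forward employment status, which the reported count makes visible.
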